### 11.6.3. Safety Analysis Set

In the safety analysis, all subjects who sign the IRB-approved written Informed Consent form will be included.

Page 87 of 177

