### ***6.6. Additional Safety Parameter***

Additional safety parameters include the following:

- Rate of occurrence of all adverse events (AEs) through End of Period 2
- Rate of occurrence of all device or procedure related adverse events (AEs), SAEs including serious adverse device events (SADEs), unanticipated adverse device events (UADEs) through end of study.

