### ***9.3. Subject Status and Classification***

Subjects who provide written informed consent but do not meet all of the study eligibility criteria will not be implanted and randomized. These subjects will be deemed as “enrolled but not randomized” and their reason for ineligibility will be documented in the EDC system. Enrolled subjects who are not randomized will not count towards the enrollment cap. Subjects who sign consent, meet all eligibility criteria, and are randomized cannot be replaced.

[REDACTED]

[REDACTED]

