### **10.2. Study Candidate Screening (Up to 60 days following Informed Consent)**

Inclusion and Exclusion criteria listed in Sections 9.2 and 9.3, respectively, will be assessed to determine study candidate eligibility. Screening is a process that includes criteria being assessed from the time of informed consent through the Period 1 Baseline Visit. The 60 day window for screening reflects the maximum timeframe from which a patient can be consented and for screening activities to begin prior to completing the medication lock visit. Subjects who have provided informed consent and who have been determined to not meet all eligibility requirements prior to randomization will be withdrawn.

[figure not shown]

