#### **10.3.1. Post-Consent Eligibility Validation**

After obtaining written informed consent, the following tests may be conducted to evaluate study-specific eligibility criteria. Study candidates not meeting the eligibility criteria will be withdrawn:

Subjects taking prescription opioids for primary chronic pain complaint (low back and/or leg pain) whose pain medications are not stable for 30 days following informed consent will be withdrawn however may be reconsented and rescreened once 30 days have passed.

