#### **10.5. Period 1 Baseline**

Period 1 baseline will last for 30 consecutive days following the Medication Lock visit. During this period, subjects will be asked to answer all questions on the eDiary daily for 30

Page 60 of 177

consecutive days beginning with the first entry the day following receipt of the eDiary. Subjects will return to the clinic with their eDiary for the Period 1 Baseline Visit.

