#### ***10.6. Period 1 Baseline Visit (0-7 days post Period 1 Baseline)***

[figure not shown]
At the Period 1 Baseline Visit, subjects will return to the office with their eDiary to evaluate their continuing eligibility in the study. Subjects that meet all study criteria will be scheduled for the device implant procedure. If subjects fail to meet all the eligibility criteria, they will be withdrawn from the study.

- **Visit Type:** In-office
- **Required Attendees:** Subject; CRC and/or Investigator
- **Study Assessments:** All required visit assessments, as outlined in Table 11-1, should be performed at the beginning of the visit.
- **eDiary:** All eDiary inclusion and exclusion criteria will be evaluated by the investigator. Subject's compliance to the fixed opioid dose will also be assessed. Subjects who do not meet required inclusion/exclusion criteria will be withdrawn. The eDiary will be reviewed during the visit and all eligible subjects will be instructed to continue completing their eDiary daily.
- **End of Visit Information:** Subjects should be reminded not to make any changes to their opioid medications (type/dose/route) and record their opioid medication use daily, as directed by the eDiary.

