## 11.6. *Analysis Sets*

All primary and secondary endpoints will be analyzed on both intent-to-treat and a per-protocol basis. Safety endpoints will be analyzed in the safety analysis set.

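### Pooled device- and implant-related event rates are taken over everyone who signs consent, so subjects withdrawn before implant dilute them

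*Combined protocol and SAP*

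**What the plan says.** Section 11.6 names three analysis sets (intent-to-treat, per-protocol and safety) and states: "Safety endpoints will be analyzed in the safety analysis set". Section 11.6.3 then defines the safety set: "In the safety analysis, all subjects who sign the IRB-approved written Informed Consent form will be included". The safety parameters in Section 6.6 include rates of device- or procedure-related AEs, SAEs including SADEs, and UADEs, through end of study.

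Consent comes well before implant, and subjects can leave in between:

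- Section 9.3: "Subjects who provide written informed consent but do not meet all of the study eligibility criteria will not be implanted and randomized".
- Section 10.2: "Subjects who have provided informed consent and who have been determined to not meet all eligibility requirements prior to randomization will be withdrawn".
- Section 10.3.1 concerns subjects on opioids "whose pain medications are not stable for 30 days following informed consent will be withdrawn however may be reconsented and rescreened".
- Section 10.5: "Period 1 baseline will last for 30 consecutive days following the Medication Lock visit". At the visit that follows (Section 10.6): "If subjects fail to meet all the eligibility criteria, they will be withdrawn from the study".

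Section 10.7 sends all subjects straight to permanent implantation without a screening trial. Section 10.9 places randomization later still, at the activation visit.

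**The concern.** A device- or implant-procedure-related event rate is read as the risk to a person who undergoes the implant. Under the stated rule its denominator also holds people who never reached the operating room and so could not have the event. The bias has a known direction: the reported rate is too low whenever at least one consented subject had no implant attempt and at least one such event occurred. Confidence limits move down and narrow for the same reason, which matters most for rare events such as UADEs. There, a reassuring upper bound would come partly from counting people who were never exposed.

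Safety is half of the primary objective in Section 5.1, so these figures will be read. The stake is limited to descriptive reporting, since no visible test or success criterion uses them.

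**Working it through.** The plan states no safety rate, sample size or screen-failure share in its legible text, so there is no figure of its own to reproduce. The check has five parts.

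**1. Time from consent to implant.** The windows are up to 60 days for screening (10.2), 30 days of baseline (10.5), 0–7 days to the Baseline Visit (10.6) and 0–14 days to implant (10.7).

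- Maximum: 60 + 30 + 7 + 14 = 111 days.
- Minimum: 0 + 30 + 0 + 0 = 30 days.

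This shows there is room for withdrawals before implant. It does not give their number.

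**2. Whether another set supplies the at-risk group.**

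- Intent-to-treat (11.6.1) holds randomized subjects only and expressly leaves out those implanted but withdrawn before randomization. Failed implants are also missing, because randomization follows implant.
- Section 9.1 refers to enrolled and randomized subjects, which omits the same two groups. Yet the same section follows failed implants for 2 weeks for procedure-related events, so they are plainly at risk.
- Section 11.9, on eligibility for evaluation, is again limited to randomized subjects.

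No legible set equals all subjects with an implant attempt.

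**3. Dilution.** Let r be the rate among implant attempts, s the share of consented subjects with no attempt, and q the rate among those never attempted. Then

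reported rate = r(1 − s) + q·s.

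For device- and implant-procedure-related events q = 0. Section 12.2.1 collects procedure-related events from consent, and the legible text does not define procedure, so a case with q = 2% is shown as well. All values of r, q and s, and the 100 attempts, are assumptions. The consented number is 100/(1 − s), rounded, and the intervals are Clopper–Pearson for 20 events.

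| s | Consented N | Rate, q = 0 | Exact 95% CI, q = 0 | Rate, q = 2% |
|---|---|---|---|---|
| 0 (attempts only) | 100 | 20% | 12.7% to 29.2% | 20% |
| 10% | 111 | 18% | 11.4% to 26.4% | 18.2% |
| 30% | 143 | 14% | 8.8% to 20.8% | 14.6% |
| 50% | 200 | 10% | 6.2% to 15.0% | 11.0% |

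For example, at s = 30%: 0.20 × 0.70 = 0.14, and with q = 2%, 0.14 + 0.02 × 0.30 = 0.146. At s = 50% the interval no longer contains the 20% rate among those at risk.

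**4. Zero events.** The one-sided 95% upper bound is 1 − 0.05^(1/N). With no UADE in 100 attempts it is 2.95%. Over 111, 143 or 200 consented subjects it becomes 2.66%, 2.07% or 1.49%.

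**5. What is not affected.** Subjects who were not randomized have no assigned sequence, so rates by sequence or therapy are not diluted in this way. All-cause AEs are collected from consent, so the consented set suits them. Listings lose no event.

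**The case against.** The strongest reply is that the argument rests on an absence in a heavily redacted document. Most of Sections 6.2–6.5 and 11.2–11.5 cannot be read, nor can 11.8, 11.10.1 and 11.10.2. The adverse-event sections cited elsewhere and Appendix A are not available either. Any of these could define a denominator. In addition, the legible text does not define a rate of occurrence. It could be per device or per unit of time on the device, and neither would be diluted. The consented set captures every event, including those in failed implants and in subjects implanted but not randomized. With ordinary disposition tables a reader could rescale the rate by one division. Finally, no document figure supports any value of s: at s = 5%, 20% would become 19%. Nor does the visible text promise confidence limits for these rates.

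Much of this stands. The size is unknown, the intervals are illustrations, and a denominator may exist in text that cannot be seen. The rest does not remove the point. The set definitions in 11.6 to 11.6.3 are legible and consecutive, and they assign safety endpoints to the consented set. Taking the named analysis set as the denominator is the natural reading. Complete capture of events is a merit for listings, but it does not make a consented denominator right for an exposure-specific risk. A reader should not have to rescale the table to obtain that risk.

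**Conclusion.** The concern holds as a minor one. On the legible text, pooled device- and implant-procedure-related AE, SADE and UADE rates are understated by the relative amount s. The direction is certain; the size cannot be computed from the documents. Over an assumed s of 10% to 50%, the reported rate is 10% to 50% too low in relative terms.

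The conclusion assumes that these rates are subject-level proportions or counts per subject in the safety set, and that no redacted passage sets another denominator. The exact (1 − s) factor applies only to device- and implant-procedure-related events. Events attributed to a study procedure before implant would soften it slightly, as the q = 2% column shows.

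**What to change.** First check whether the unredacted plan already gives a denominator for these rates. If it does not:

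- Keep the consented set for listings and all-AE summaries.
- Add a set of all subjects with an implant attempt, including failed implants and subjects implanted but not randomized, as the denominator for pooled device- and implant-procedure-related AE, SADE and UADE rates.
- Show the numbers consented, attempted, implanted and randomized beside each rate. Count a rescreened person once, since Section 10.3.1 allows a second consent.
- List separately any event attributed to a study procedure before implant.

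The cost is one set definition in the SAP and one extra column in the safety tables. No new data are needed, because implant procedures are already recorded (Section 12.2.18). The drawbacks are less favourable reported rates and two denominators that must be clearly labelled.

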#### **11.7. Control of Systematic Error/Bias**

Selection of patients will be made from the Investigator's usual patient load. All patients meeting the inclusion/exclusion criteria and having signed the Informed Consent Form will be eligible for participation in the study. The reasons for exclusion, for subjects who sign an informed consent form but are not randomized, will be indicated in the screening log. Consequently, consecutively eligible subjects will be randomly allocated into the study, minimizing selection bias. Boston Scientific will report to the FDA any evidence of fraud, including deliberate tampering with the selection of subjects.

[REDACTED]

[REDACTED]

[REDACTED]

#### **11.9. Eligibility of Subjects, Exclusions, and Missing Data**

All subjects who are randomized will be eligible for evaluation. Sensitivity analyses will be conducted to assess the impact of different assumptions on the interpretation of the results. For continuous covariates, the missing/unknown values will be imputed using the mean of the pooled observed data. For categorical covariates, the missing/unknown values will be combined with the category with the most subjects if the missing/unknown rate is  $\leq 2\%$  of the pooled observed data, or they will be classified into a separate category if the missing/unknown rate is  $> 2\%$  of the pooled data. If the covariates are also used as subgroup variables, the imputed values of subgroup variables will not be used for subgroup categorization.

[REDACTED]

[REDACTED]

[REDACTED]

[REDACTED]

[REDACTED]

## 11.10. *Data Analyses*

All statistical analyses will be done using the SAS System software, version 8.2 or later (Copyright © 2000 SAS Institute Inc., SAS Campus Drive, Cary, North Carolina 27513, USA. All rights reserved).

### 11.10.3. *Justification of Pooling*

Analyses will be performed using data pooled across various sites/institutions. Multivariate analysis techniques, including contingency tables and logistic regression for binary outcomes

Page 89 of 177

and analysis of variance for continuous measures, will be used to assess differences among study sites to justify pooling data across sites.

[REDACTED]

Page 90 of 177

### **11.11. *Changes to Planned Analyses***

Changes from the planned statistical methods after performing the analyses will be documented in the clinical study report along with a reason for the deviation.

## **12. Data Management**

### **12.1. *Data Collection, Processing, and Review***

Subject data will be recorded in a limited access secure electronic data capture (EDC) system.

The clinical database will reside on a production server hosted by Medidata. All changes made to the clinical data will be captured in an electronic audit trail and available for review by Boston Scientific Corporation (BSC) or its representative. The associated RAVE software and database have been designed to meet regulatory compliance for deployment as part of a validated system compliant with laws and regulations applicable to the conduct of clinical studies pertaining to the use of electronic records and signatures. Database backups are performed regularly.

The Investigator provides his/her electronic signature on the appropriate electronic case report forms (eCRFs) in compliance with local regulations. Changes to data previously submitted to the sponsor require a new electronic signature by the Investigator acknowledging and approving the changes.

Visual and/or electronic data review will be performed to identify possible data discrepancies. Manual and/or automatic queries will be created in the EDC system and will be issued to the site for appropriate response. Site staff will be responsible for resolving all queries in the database in a timely manner.

#### **12.1.1. *Electronic Diary (eDiary)***

Subjects who meet the applicable Inclusion and Exclusion criteria will be given an eDiary to capture daily assessments once a day of average low back pain intensity, average leg pain intensity, worst low back pain intensity, worst leg pain intensity, opioid medication intake, and device charging information.

Diary entries will be collected daily for each morning-to-night period. The eDiary will be automatically unlocked for data entry each evening at approximately 7 PM. At this time, an alarm will sound to ask subjects to report information for that day. Once the subject enters the required information, the eDiary will be automatically locked until the following evening. If the subject fails to enter the required information by approximately 3 AM, the eDiary will

Page 91 of 177

be automatically locked until the following evening, and the data for that day will be classified as missing.

The eDiary consists of a small, handheld computer programmed specifically for this study. Data entry is interactive and based on a series of questions and is dated and time stamped. Data will be uploaded to a central computer resource. Specific training materials for the use of the eDiaries will be provided to each study subject.

The eDiary data are critical to endpoint analysis in this study. Thus, subjects who are non-compliant will be counseled by site staff as to the importance of daily entries.

#### ***12.1.2. Paper Questionnaires***

Data from paper forms may be collected from the site using fax and automatic character recognition. Paper forms and questionnaires are completed by the subject or a clinician and then sent via facsimile from the site. When the forms are received, each page is automatically scanned and indexed by intelligent character recognition (ICR) software, and uploaded into the EDC system.

#### ***12.1.3. Electronic Questionnaires***

Questionnaires in electronic form may be collected directly using an electronic data collection platform at the clinical site (e.g. iPad). After completion by the subject or a clinician, data from the electronic questionnaires are transmitted directly into the EDC system.

#### ***12.1.4. Direct Data Upload***

For quality assurance purposes and validation, technical data on the SCS device, stored in the BSC Field Clinical Engineer/Field Clinical Specialist's (FCE) Clinician Programmer, will be collected using direct data upload to a secure BSC server. BSC FCEs, who assist in programming the device settings per routine care, will upload the Clinician Programmer database files to a secure server stored in a restricted location at BSC.

### ***12.2. Study Assessments***

#### ***12.2.1. Adverse Events***

Adverse event evaluation will be conducted to identify adverse events occurring during the study and classify them in regards to seriousness, relationship to the study procedure and/or device, action taken and outcome. Safety events will be reported as specified in Table 20-3.

- Non-serious AEs which are neither device/procedure related will be collected from the time of informed consent through the end of period 2.
- Adverse events which are device/procedure related will be collected from the time of informed consent through 12 months post-Period 1 activation

Page 92 of 177

- SAEs, SADEs, Device Deficiencies and UADEs will be collected from the time of informed consent through 12 months post-Period 1 activation.

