## 2. Primary Protocol Synopsis\*

\*For subjects enrolled during protocol AA-AG. All new subjects will be enrolled under the extension (sub-study) protocol in Appendix A.

ACCELERATE A Randomized Controlled Study to Evaluate the Safety and Effectiveness of the Precision Spinal Cord Stimulator System Adapted for High-Rate Spinal Cord Stimulation	
Primary Objective	To evaluate the safety and effectiveness of high rate spinal cord stimulation (HR-SCS) therapy as compared to commercial rate spinal cord stimulation (CR-SCS) therapy as an aid in the management of chronic intractable pain of the trunk, including unilateral or bilateral pain associated with the following: failed back surgery syndrome, intractable low back pain using the Boston Scientific (BSC) PRECISION Spinal Cord Stimulator System Adapted for High-Rate Spinal Cord Stimulation (PRECISION SCS System for HR)
Secondary Objective	To determine the impact of HR-SCS therapy on global patient outcomes as an aid in the management of chronic intractable pain of the trunk and/or limbs, including unilateral or bilateral pain associated with the following: failed back surgery syndrome, intractable low back pain and leg pain using the Boston Scientific (BSC) PRECISION SCS System for HR
Planned Indication(s) for Use	The BSC PRECISION SCS System for HR is indicated as an aid in the management of chronic intractable pain of the trunk, including unilateral or bilateral pain associated with the following: failed back surgery syndrome or intractable low back pain.
Test Parameters	BSC PRECISION SCS System for HR: Stimulation rate: locked at 10kHz during crossover period, 2-1200 Hz or 2KHz – 10KHz during long-term follow-up period
Control Parameters	BSC PRECISION™ SCS System: Stimulation rate: Commercially Approved range (2-1200 Hz)
Study Design	Multi-center, randomized, controlled, non-inferiority, crossover, adaptive, open label

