#### **10.18. *End of Period 2 Visit (90 ± 14 days post-Period 2 Baseline/Activation Visit)***

This visit will represent the End of Period 2 and subjects will begin long term follow up after completion of this visit. Subjects will choose to either receive HR-SCS or CR-SCS therapy for the rest of the study and may not change once chosen. Programming will be done only after all the required assessments are completed.

- **Visit Type:** In-office
- **Required Attendees:** Subject; CRC and/or Investigator; Field Clinical Engineer/Field Clinical Specialist or designee
- **Study Assessments:** All required visit assessments, as outlined in Table 11-1, should be performed at the beginning of the visit.
- **Device Programming:** Following the completion of all End of Period 2 Visit assessments and procedures, subjects will choose whether to receive HR-SCS or CR-SCS therapy until the End of Study Visit. The device may be reprogrammed in accordance with Section 11.21.3 and the treatment parameters selected by the subject. Program settings must be documented in the study records.
- **eDiary Collection:** The eDiary must be collected from the subject along with all eDiary peripherals. Subjects no longer need to complete the eDiary.
- **End of Visit Information:** Subjects will receive instructions on the use of the device including Remote control and charging system as needed
  - Subjects are to contact the site in an event that any additional intervention is warranted, to report a complaint and/or a suspected adverse event, reprogramming, etc.
  - Subjects should be reminded to charge their Precision SCS system as needed. It is recommended that they check the status of their battery using their remote control

Page 69 of 177

- Subjects' opioid medications can be changed, if needed for the remainder of the study. .

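### Rates of 2 to below 10 kHz are first allowed when collection of non-serious unrelated adverse events has ended, so all-AE collection covers none of that exposure

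*Combined protocol and SAP*

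**What the plan says.** Section 2 (Test Parameters) sets the high-rate system's stimulation rate by phase: "locked at 10kHz during crossover period, 2-1200 Hz or 2KHz – 10KHz during long-term follow-up period". The control stays within 2-1200 Hz. Section 10.18 fixes the moment of change: "This visit will represent the End of Period 2 and subjects will begin long term follow up after completion of this visit". Subjects then choose high-rate or commercial-rate therapy; Section 12.2.8 also allows for neither.

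Section 12.2.1 sets three collection windows:

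- The shortest applies to events that are neither serious nor related: "Non-serious AEs which are neither device/procedure related will be collected from the time of informed consent through the end of period 2".
- A longer one applies once an event is judged related, whether serious or not: "Adverse events which are device/procedure related will be collected from the time of informed consent through 12 months post-Period 1 activation".
- The last has the same 12-month limit and covers serious events, serious or unanticipated device events, and device deficiencies.

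Section 6.6 mirrors this split. One parameter is "Rate of occurrence of all adverse events (AEs) through End of Period 2"; the other covers related AEs and serious or unanticipated events to the end of the study. Section 7 states that subjects, site personnel and the sponsor are all unblinded.

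**The concern.** Narrowing AE collection late in a device study is defensible when subjects remain on settings already observed under full collection. Here the narrowing coincides with the opening of a new part of the investigational rate range. From that visit on, a non-serious event is required in the database only if it is judged related to the device or procedure. A filter of this kind loses an effect that nobody yet recognises as an effect.

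The stake is how far the safety statement can reach. The primary objective (Section 5.1) covers the safety of HR-SCS with this system, the synopsis lists 2-10 kHz among the test parameters, and the readable planned indication is for the system without a limit to 10 kHz. Commercial rates have all-AE data from the crossover, and so does 10 kHz. In the readable text, 2 to below 10 kHz has none. The primary effectiveness comparison is not affected.

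**Working it through.** The plan gives no figure of its own for this exposure, so the check adds up the visit schedule in Section 2 (repeated in Sections 10.12 to 10.19). Days are counted from Period 1 activation.

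Inputs: Period 1 lasts 90 ± 14 days; washout 7; Period 2 baseline 15; 0-7 further days to Period 2 activation; Period 2 lasts 90 ± 14; End of Study is at day 365 ± 30.

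End of Period 2 = Period 1 + 7 + 15 + (0 to 7) + Period 2:

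- Earliest: 76 + 7 + 15 + 0 + 76 = day 174
- Nominal: 90 + 7 + 15 + 0 + 90 = day 202, or day 209 with the 7 extra days
- Latest: 104 + 7 + 15 + 7 + 104 = day 237

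Long-term period = End of Study − End of Period 2:

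- Shortest: 335 − 237 = 98 days
- Nominal: 365 − 209 = 156 to 365 − 202 = 163 days
- Longest: 395 − 174 = 221 days
- Nominal share of 365 days: 156/365 = 42.7% to 163/365 = 44.7%

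The rules by phase then line up as follows:

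- **Crossover.** Rates allowed: 10 kHz or 2-1200 Hz. All AEs are collected. A subject who completes the high-rate period has about 90 days (76-104) at 10 kHz under this rule.
- **Long-term.** Rates allowed: 2-1200 Hz or 2-10 kHz. Collection covers related AEs, SAEs, SADEs, UADEs and device deficiencies.

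The days on which 2 to below 10 kHz is permitted and all AEs are also collected number 0. The 156-163 days are permitted exposure, so they are an upper limit on the nominal schedule: a subject may choose commercial rates or neither, or stay at 10 kHz. The number of subjects who will use the intermediate rates is not fixed anywhere in the readable text. The number of events that would go unrecorded cannot be calculated from the documents.

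**The case against.** The strongest reply is that this is a declared and internally consistent choice. Sections 6.6 and 12.2.1 agree with each other. Related AEs are kept to 12 months whether serious or not. Subjects are told at End of Period 2 to report suspected AEs, and Section 10.20.2 provides for unscheduled visits to evaluate them. The long-term phase is self-selected with no randomised comparator, so extra unrelated non-serious events would be hard to attribute to rate.

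Much of this stands. It narrows the gap to non-serious events that are not recognised as related, and it limits what extended collection could prove. It does not change the coincidence of dates: an unrelated-judged event reported at an unscheduled long-term visit still falls outside the collection rule.

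Three stronger readings are tempting but not supported:

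- **That AE rates at the new settings will look artificially low beside the crossover.** No readable passage plans an all-AE comparison of long-term with crossover rates. Related and serious events follow one rule from consent to 12 months, so comparisons of those remain like for like.
- **That an unblinded investigator alone decides what is recorded.** Section 12.2.1 does not say who judges relatedness. Section 12.2.10 names the investigator for neurological change only, and the safety-reporting section and Table 20-3 are not in the supplied text. The site is unblinded in any case. Independent adjudication, if it exists, could not recover events that were never entered.
- **That open-label judgement leads to under-attribution.** Nothing in the documents shows the direction; knowing the setting could equally raise attribution.

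**Conclusion.** The point holds as a limit on the safety evidence. By rule, no permitted use of 2 to below 10 kHz falls under all-AE collection; the period concerned is nominally 156-163 days (98-221 at the window extremes, about 43-45% of 365 days nominally). What is missing is non-serious events at these rates that the unblinded site does not recognise as related. Serious events, related events, UADEs and device deficiencies are still captured. A reader might infer that long-term safety is not monitored or that planned safety comparisons are biased; the documents support neither.

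This rests on the primary protocol for subjects enrolled under versions AA-AG. The programming rules in Section 10.22 are not readable and the extension protocol in Appendix A is not supplied, so it is not known whether either narrows the long-term rates or changes AE collection. The change is a worthwhile improvement at low cost and does not bear on the primary effectiveness test.

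**What to change.** In Sections 12.2.1 and 6.6, extend collection of all AEs, whatever their relatedness, to the End of Study visit. Apply this to all subjects in the long-term period, so that those who choose commercial rates are collected under the same rule. Collect at End of Study and at any unscheduled long-term visit or contact. The readable schedule shows no planned visit in between, so the text should acknowledge that ascertainment will be less intensive than in the crossover.

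Tabulate long-term AEs by the rate band programmed at onset (commercial, 2 to below 10 kHz, 10 kHz), using the programming data already captured under Sections 12.1.4 and 12.2.19, and label the table non-randomised.

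If collection is not extended, state that the all-AE safety conclusion for HR-SCS applies to 10 kHz only, and that evidence for 2 to below 10 kHz is limited to related and serious events and device deficiencies. This alternative needs only wording.

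The cost of extension is a protocol text change, roughly five more months of non-serious AE entry per subject (156-163 days), more AE forms and a higher raw AE count.
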